### **Intervention description {11a}**

#### *Experimental condition*

The NCFP intervention is delivered by nurses and community health workers (CHWs) as part of a collaborative partnership with households over the course of 5 months. On average, there will be three nurse-CHW home visits to households randomized to the intervention condition per month. Each visit will last for approximately 45 minutes on average.

The NCFP intervention prioritizes provision of intervention content based on three household risk levels: low, medium, and high. This intervention will use an algorithm to determine household-level risk to COVID-19. Low risk is defined by experience of no symptoms and no exposures by all household members. Medium risk is defined by experience of either symptoms (i.e. new cough, chest pain, fever above 100.4°, and/or loss of taste or smell) or an exposure to someone with known or suspected COVID-19 by any household member. High risk is established when a household member has a confirmed positive COVID-19 test. The algorithm will be informed by self-report of symptoms and exposures through a nurse hotline that is available for households placed in the intervention arm to use.

Additionally, nurses will conduct weekly phone screenings to continue monitoring household symptoms and exposures. For households that are at low risk, the intervention delivery team will provide the standard intervention content, which consists of (1) development and follow-up of an infection control plan tailored to the unique circumstances of the household, (2) printed NCFP family materials, (3) offer of monthly routine Polymerase Chain Reaction (PCR) COVID-19 test (self-administered saliva test), (4) provision of PPE (masks, hand sanitizer, gloves) and a thermometer, and (5) navigation to at-home or community-based COVID-19 vaccination services, as well as health, social welfare, vocational,

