### **Outcomes {12}**

The primary outcome of interest is the following:

1. Household COVID-19 testing

Household COVID-19 testing uptake at the 9-month follow-up (9MFU) will be the primary outcome of interest. Our project will document testing uptake that is either administered by nurses or self-administered during home visits in the experimental arm, as well as self-reported information regarding COVID-19 testing uptake by study participants in the treatment and control groups. Participants will be asked whether they have received COVID-19 testing in the past three months, as well as about variables collected via the COVID-19 Symptoms, Diagnoses, and Testing scale. The COVID-19 Symptoms, Diagnoses, and Testing scale is adapted from the COVID-19 Cannabis Health Questionnaire. Specifically, participants will be asked questions regarding whether they are currently sick with an illness that might be related to COVID-19, any symptoms the participant experienced in the past three months, and the result of the participant's last COVID-19 test.

The secondary outcomes of interest are:

1. Household COVID-19 Testing Uptake

All medical services delivered by nurses during home-visits (such as COVID-19 test administration) will be carefully documented by the investigative team. At the time of the 6-month-follow-up (6MFU) assessment, the project team will obtain self-reported information regarding COVID-19 testing uptake by study participants in the treatment and control groups. Respondents will be asked whether they have received COVID-19 testing in the past six months. Respondents will also be asked questions from the COVID-19 Symptoms, Diagnoses, and Testing scale regarding whether they are currently sick with an illness that might be related to COVID-19, any symptoms the participant experienced in the past six months, and the result of the participant's last COVID-19 test.

2. COVID-19 control measure uptake

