COVID-19 control measure uptake will be assessed using the COVID-19 Knowledge, Attitudes, and Avoidant Behaviors section of the Understanding America Study. Respondents will be asked questions on a 5-point Likert scale (Almost Never to Always), with higher values representing greater uptake of COVID-19 prevention behaviors (e.g., "Had close contact (within 6 feet) with people who do not live with you. "Gone out to a bar, club, or other place where people gather) and COVID-19 control uptake (e.g., "Worn a mask or other face covering." "Washed your hands with soap or used hand sanitizer several times per day"). COVID-19 control measure uptake will be assessed at the immediate follow-up (6 months) and at the delayed follow-up (9 months).

3. Vaccine Uptake

The investigators will obtain self-reported information and documentation of influenza and COVID vaccine uptake by study participants at the 6-month and 9-month follow-up assessments. Respondents will be asked if they received the flu shot [Yes/No] and whether they received the COVID-19 vaccine [Yes/No], the type of vaccine, and the number of doses.

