## **Trial Status**

*Trials* guidance: Authors should report the protocol version number and date, the date recruitment began, and the approximate date when recruitment will be completed.

Protocol Version 1: \_\_\_\_\_

Recruitment Start Date: July 23rd, 2021

Current Status: Recruiting

Anticipated End Date: July 31, 2022

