COVID-19 control measure uptake, which is adapted from the COVID-19 Knowledge, Attitudes, and Avoidant Behaviors section of the Understanding America Study (CESR, 2020). Respondents will be asked questions regarding their engagement in behaviors associated with COVID-19 exposure on a 5-point scale [Almost Never, Sometimes, a Moderate Amount of the Time, Most of the Time, Always]. Greater values indicate higher frequency of uptake of COVID-19 prevention behaviors (e.g. "Canceled or postponed social activities." "Avoided riding the bus or subway") This questionnaire also includes questions regarding their uptake of COVID-19 control measures such as PPE usage and hand washing or sanitation. This will be measured both in immediate follow up (6 months), asking the participant to recall the past six months and also in delayed follow-up (9 months), asking the participant to recall the past three months.

Household COVID-19 Testing Uptake will be assessed as above, however at the immediate follow up time point (6 months). At the 6-month follow up point, participants will be asked whether they have received COVID-19 testing in the past six months [Yes/No]. Further, the COVID-19 Symptoms, Diagnoses, and Testing Scale will be administered at six months. Questions will ask respondents whether they are currently sick with an illness that might be related to COVID-19, any symptoms the participant experienced in the past six months [Check All That Apply], and the result of the participant's last COVID-19 test [Positive/Negative].

Vaccine Uptake will be documented by the study team via seasonal influenza and COVID-19 vaccination referrals by study nurses. Investigators will obtain self-reported information and documentation of influenza vaccine uptake by participants in both treatment arms by asking participants if they have received the influenza vaccine at the 6-month and 9-month follow up assessments [Yes/No] and whether they received the COVID-19 vaccine [Yes/No], the type of vaccine, and the number of doses.

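### The influenza vaccine outcome has no date, season or since-randomisation limit, so shots taken before randomisation can count as uptake and dilute the arm difference

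*Protocol*

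**What the plan says.** Protocol, Outcomes {12}, Vaccine Uptake, plans to obtain "self-reported information and documentation of influenza and COVID vaccine uptake by study participants at the 6-month and 9-month follow-up assessments". The flu item itself is: "Respondents will be asked if they received the flu shot [Yes/No". For the COVID-19 vaccine the type and number of doses are also asked; for influenza nothing further is asked. The SAP, Definition of Secondary Outcomes, repeats the item: "asking participants if they have received the influenza vaccine at the 6-month and 9-month follow up assessments [Yes/No".

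The testing outcome, by contrast, has a look-back at each visit. At month 6, "Respondents will be asked whether they have received COVID-19 testing in the past six months"; at month 9, "Participants will be asked whether they have received COVID-19 testing in the past three months". The SAP gives the same six- and three-month windows for control measures and for mutual aid.

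Protocol, Trial Status, gives "Recruitment Start Date: July 23 rd , 2021" and "Anticipated End Date: July 31, 2022". The intervention (Protocol {11a}) is a "collaborative partnership with households over the course of 5 months".

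Influenza uptake is part of the study hypothesis in Protocol, Trial design {8}, and again under the choice of comparators {6b}. Both places call the vaccine seasonal.

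**The concern.** The follow-up clock runs from each household's baseline, while influenza vaccination follows the calendar. With about a year of enrolment the two drift apart. An undated Yes can then be a shot taken before randomisation, one taken during the intervention, or one taken in the next season after visits ended. The data as specified cannot separate these.

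Shots taken before randomisation add the same expected amount to both arms and none of it is attributable to the intervention. They shrink the difference on a stated hypothesis. A null result could mean that the intervention did not move vaccination, or that many participants had already been vaccinated, and the trial could not tell which.

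**Working it through.** **The plan's own figure.** The only power statement (both documents) is above 80% for a difference of 0.15 from a control proportion of 0.10. It reproduces. The design effect is 1 + (3 − 1)×0.7 + 3×(2 − 1)×0.3 = 3.3, so the effective sizes are 600/3.3 = 181.8 and 300/3.3 = 90.9. Two-sided power is about 86% at full size and about 80% after 15% attrition (pooled variance). It does not name influenza, so its 0.10 and 0.15 are not used below.

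**Dilution.** Let q be the share of each arm vaccinated before randomisation, and let a and b be uptake after randomisation among the rest (control, intervention). The item records

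- control: q + (1 − q)a
- intervention: q + (1 − q)b
- difference: (1 − q)(b − a)

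For q = 0.1, 0.2 and 0.4, the share of the true difference that remains is 90%, 80% and 60%. These q values are illustrative.

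**Calendar inputs.** The start is 23 July 2021 and the end 31 July 2022, both inclusive, which is 374 enrolment days. Two things are assumed because the documents do not give them: even accrual, and the months of vaccination, for which a range is shown. Six months is counted as 183 days and nine months as 274.

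**Could a shot precede randomisation?** From 23 July to 31 August 2021 is 9 + 31 = 40 days, leaving 374 − 40 = 334 on or after 1 September. 334/374 = 89%. If vaccination opens on 1 September, an earlier shot that season was possible for these households. This is an upper limit on opportunity, not an estimate of q.

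**Households with no vaccination period between randomisation and the visit.** These enrol after the 2021-22 period closes and are visited before 1 September 2022. For month 6 the last such enrolment day is 1 March 2022; for month 9 it is 30 November 2021.

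| Assumed period | No overlap by month 6 | No overlap by month 9 |
|---|---|---|
| Sep-Oct | 121/374 = 32% | 30/374 = 8% |
| Sep-Nov | 91/374 = 24% | 0% |
| Sep-Dec | 60/374 = 16% | 0% |
| Sep-Jan | 29/374 = 8% | 0% |
| Sep-Mar | 0% | 0% |

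Counting each interval one day shorter moves the Sep-Nov row to 25% and 0.3%.

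**Do months 6 and 9 straddle two seasons?** For enrolment from 1 December 2021 to 1 March 2022, month 6 falls before 1 September 2022 and month 9 on or after it. That is 91 of 374 days, 24%. A household enrolled on 26 January 2022 is asked about 28 July and again about 27 October 2022, the second time in a new season if vaccination opens in September.

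**The end date.** It is not labelled. The template line above it asks when recruitment will be completed, the status is still recruiting, and the references include sources accessed in January 2022. If it were instead the end of follow-up, the last enrolment would be about 30 October 2021. Then 60 of 100 enrolment days would still fall on or after 1 September.

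**The case against.** **The plan may already hold the missing information.** Protocol {18a} lists seasonal influenza uptake among the contents of surveys given at eight time points, baseline included. The SAP (Created Variables) plans differences from baseline and names vaccination status as an example. Its Framework section compares baseline with month 9. Vaccine documentation may carry dates. If flu status is captured at baseline, a person already vaccinated shows no change and is not a new success. So it is not established that every earlier shot would be counted. But no baseline flu item, date or rule is written down, and the SAP's baseline vaccination question (Confounding Variables) sits beside prior COVID-19 diagnosis without naming influenza. Change scores alone also fail for someone who answers Yes at baseline for one season and Yes later for a new shot: the score is zero.

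**Stronger readings that the documents do not support.** A reader might infer that households whose five-month intervention misses the vaccination months cannot respond, and so take off a fixed fraction of the effect. Non-overlap with the intervention is 33% for Sep-Nov (122/374) but about 0% for Sep-Mar. Moreover, the inference needs the effect to stop when visits stop. The SAP's mediation section instead assumes that effects persist, with possible lagged effects on month-9 outcomes, and by month 9 almost every household has met some vaccination period. A reader might also infer systematic bias. Households are randomised, so enrolment date and earlier shots balance in expectation.

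What stands of the objection is that the size is unknown and the harm is limited to one component of one secondary outcome.

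**Conclusion.** The point holds as a gap in the outcome definition. As written, the influenza item admits shots taken before randomisation and does not tie a Yes to a season; nothing specified elsewhere prevents this. The result is attenuation by (1 − q) and a result that is hard to interpret.

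The size cannot be fixed from the documents, because q, the vaccination months and the accrual pattern are all missing. Under even accrual, up to about 89% of households could have had an earlier shot that season. No overlap between follow-up and a vaccination period affects 0 to 25% by month 6 (Sep-Mar to Sep-Nov) and essentially none by month 9; only a two-month Sep-Oct period gives more (32% and 8%). The ambiguity about which shot is meant remains at both visits. The primary outcome is unaffected.

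**What to change.** - Ask the month and year of the last influenza shot at months 6 and 9, and at baseline for households still to enrol. For the others, take prior vaccination from recall or from the vaccine documentation already being obtained.
- Define the outcome as an influenza shot dated after randomisation.
- Analyse all randomised households by intention to treat, in line with Protocol {20c}. Do not restrict the main estimate to households whose intervention overlaps a season: that would demote the all-household result and depend on vaccination months the plan does not state.
- Adjust for enrolment period and, where known, for influenza vaccination before randomisation.

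The cost is one survey field, some SAP wording and some recall error in dates. Timing limits what can be recovered. Reading the SAP date as 12 July 2022 and assuming even accrual, only 20/374 = 5% of households were still to enrol, but about 78% of month-9 visits (293/374) were still to come.

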### **Sample size {14}**

Power for the proposed study was calculated using Power Analysis and Sample Size software based on household level randomization, individual level outcomes using conservative estimates and adjusting for 15% attrition and allowing for subgroup analyses. A test for the difference in two proportions using a mixed model based on a clustered 3-Level Hierarchical Design with level-3 (household) 2:1 intervention: control randomization. The total sample size of 300, obtained from 100 level-3 units (households) in the intervention group and 50 level-3 units in the control group with an average of 2 level-2 units (individuals) per level-3 unit (household) and an average of 3 level-1 units (timepoints) per level-2 unit (individual), achieves >80% power to detect a difference between the group proportions of at least 0.15. The proportion in group 2 is 0.10. The correlation of level-1 units within a level-2 unit is <0.7. The correlation of level-2 units within a level-3 unit is <0.3. A test based on a mixed-effects logistic regression is anticipated at a significance level of 0.05.

### **Recruitment {15}**

Recruitment from randomly selected households will begin with canvassing, when flyers will be placed in the building announcing the study. Study staff will talk to residents in the lobbies and courtyards about the opportunity to participate. Once study staff have adequately established their presence, the study recruitment team will move forward with door-to-door recruitment of randomly selected households. Once potential participants open their front door, the recruitment team will take the opportunity to explain the study. For interested households, the recruitment team will administer a screening questionnaire to assess their initial eligibility. If households are eligible and interested to enroll into the study, they will move forward to the consent process.

### **Assignment of interventions: allocation**

#### Sequence generation {16a}

The allocation sequence will be generated using a computer algorithm prior to the begin of study enrolment.

### **Concealment mechanism {16b}**

The allocation sequence will be coded into REDCap where it will only be visible to the REDCap data management team.

### **Implementation {16c}**

Households that are enrolled into the study will be entered into the REDCap database, which automatically assigns a study ID. REDCap assigns the household study ID to either the experimental or control condition using the pre-generated and coded sequence. After completion of the baseline assessment (assessors are blinded), the REDCap data manager notifies the NCFP intervention team of new households that have been assigned to the experimental condition. The intervention team then contacts the household to begin the NCFP intervention program.

### **Assignment of interventions: Blinding**

#### **Who will be blinded {17a}**

The statistician and physicians that comprise the Data Safety Monitoring Board (DSMB) will be blinded to the allocation. Additionally, all study staff members who are involved with scheduling, coordinating, and implementing data collection will be blinded to the allocation (assessor blinded).

#### **Procedure for unblinding if needed {17b}**

In this trial, participants will be aware of the study condition they were assigned to. As such, procedures for unblinding will not be needed.

#### Data collection and management

#### **Plans for assessment and collection of outcomes {18a}**

Data will be collected at eight time-points: baseline, monthly during months 1-6 of the study, and at 9 months post-baseline. Participants will complete self-reported surveys that assess basic demographics such as birthdate, age, gender, race/ethnicity, educational attainment, etc. In addition to collecting basic demographics, the study surveys will contain items and scales from the PhenX Toolkit and the NIH Disaster Response website. These survey items and scales will assess participants' household-level

COVID-19 routine testing, household-level COVID-19 indicated testing, COVID-19 vaccine uptake, adoption of COVID-19 control measures, household-level mutual aid capacity, and seasonal influenza vaccine uptake. All survey items developed by our team will be shared with the Rapid Acceleration of Diagnostics Underserved Populations (RADx-UP) Coordination and Data Collection Center and made public. Data will be collected via tablets that will be programmed in REDCap. Surveys are available in English and Spanish to facilitate, survey data collection. The survey may be self-administered or, in the case of low literacy or lack of familiarity with electronic devices, data collection staff will read prompts and record survey responses onto the tablets. Mode of administration will be recorded for later analysis of potential bias. To reduce social desirability bias, CHWs and nurses who deliver the NCFP intervention will not take part in the data collection process. Rather, data collection will be conducted by dedicated staff who are trained in survey research methods and human subject protections, including confidentiality. Additionally, social desirability tendency will be assessed using designated items in the study surveys. Furthermore, we will record participation rates for each household by member.

#### **Plans to promote participant retention and complete follow-up {18b}**

During the consent process, the study team will obtain extensive tracking information, including phone numbers, email addresses, and home addresses. Participants will be asked to provide contact information for three people who know how to reach them in most circumstances. These methods were used in previous work in the South Bronx with an attrition rate of 8% over 12 months [17]. Prior experience indicates that virtually all respondents will have a cell phone or access to a phone. However, as part of the consent process, we will obtain permission to revisit the home to make follow-up appointments if phone contact is not possible. Additionally, we will allow for flexibility in scheduling by conducting reminder calls before scheduled data collection appointments.

#### **Data management {19}**

In accordance with the NIH requirements, the clinical trial created a data and safety monitoring plan to protect participants' privacy and confidentiality during the study. A DSMB will be established and be in

direct communication with the relevant program officer at NIH. The DSMB will be comprised of at least 4 individuals (with a designated committee chair), who represent expertise in bioethics, statistics/methodology, medical testing, vaccinations, and research knowledge in COVID-19 and infection control.

Data will be collected by trained and supervised staff members on tablets that are programmed in REDCap. Access to the project's offices are restricted to faculty and staff. The building is secure and monitored by security staff. File drawers containing participant information are kept locked when not in use. Only project staff members have keys to these file cabinets. Only the consent forms, locator forms, and computerized tracking database link the participant's name to the identification number. The computerized tracking database is kept on a password-protected folder on the NYU server, which requires a separate password to be accessed. Staff who are not members of the research team for this study do not have access to this folder. All computerized data (survey data, transcripts, and biological specimen results) are kept on computers that are double-password protected and files are only labeled with participant identification numbers. Files are sent to the NYU share drive for back-up, which is also double password protected and available only to project staff. A master database that contains participant identifying information and participant identification (PID) numbers is kept on the internal NYU share drive. This folder is double password protected and can only be accessed by the study's staff members.

